#### **Initial human safety, tolerability, and PK results from MP0420-CP101**

The safety-focused no-observed-adverse-effect-level (NOAEL) approach was used to determine FIH doses of 3, 9 and 20 mg/kg for MP0420-CP101 (summary of the relevant pre-clinical safety data can be found in the Investigator's Brochure [IB]). Dosing of healthy volunteers with single i.v. infusions of 3 and 9 mg/kg (8 mg/kg would equate to a single dose of 600 mg in a 75 kg person) was completed. MP0420-CP101 Phase 1 investigation of the safety, tolerability, and PK of MP0420 in healthy participants is ongoing, and to date MP0420 was assessed as safe and well-tolerated and no serious adverse effects have been reported. A 20 mg/kg cohort will be enrolled in Q1 2021. Based on this, the proposed doses of 75, 225, and 600 mg are expected to be safe in SARS-CoV-2 infected patients.

Preliminary PK data from cohort 1 (i.v., 3 mg/kg) and cohort 2 (i.v., 9 mg/kg) are available. The estimated half-life for MP0420 across cohorts is approximately 14.4 days (mean, range: 11.4-24.0 days). Slightly greater than dose-proportional increases in exposure were observed from cohort 1 to cohort 2 (3.8-fold increase in AUC with a 3-fold increase in dose). Cohort 1 exhibited serum concentrations on Day 14 of  $31.9 \pm 6.3$  ug/mL (mean  $\pm$  standard deviation [SD]), which corresponds to  $378 \pm 75$  nM (mean  $\pm$  SD), and is  $> 1000$ -fold above the IC50 determined for MP0420 in infected Vero E6 cells. Cohort 1 exposures approximate the 225 mg single dose, which is the mid-dose in this dose-range finding study.

### **PK/PD modeling**

The PK/PD model was constructed from publicly available data describing viral kinetics from SARS-CoV-2 patient throat swabs from untreated COVID-19 patients and calibrated to describe reported viral load data from patients treated with a neutralizing antibody therapeutic (LY-CoV555). The PK/PD model accounts for MP0420 PK, binding affinities, and MoA to predict effects in the lung. Simulations from the PK/PD model indicate that near-maximal binding of SARS-CoV-2 RBD is observed for MP0420 with a single, i.v. dose of 75 mg ( $> 95\%$  reduction in free viral spike protein AUC), which is expected to correlate with clinical efficacy. Due to uncertainties in both the modeling predictions and the severity of disease at onset of therapy it is recommended that 75 mg, 225 mg, and 600 mg doses should be tested as part of a dose-range finding study in SARS-CoV-2 infected patients.

### **4.3 Rationale for choice of control drug (placebo)**

Given that no products have received full approval for the sponsor's intended label claim, the sponsor proposes that placebo is the most appropriate comparator for this study. This approach is best scientific practice and has been endorsed by regulatory authorities in United States of America and Europe at recent Health Authority interactions.

### **4.4 Purpose and timing of planned analyses/design adaptations**

Additional interim analyses may be conducted to support decision making concerning the current clinical study, the sponsor's clinical development projects in general, or in case of any safety concerns.

Additional information is presented in the interim analysis section.

### **Part A**

A primary analysis based on viral load up to Day 8 is planned. This analysis is planned after all patients have completed the Day 29 visit. Additional unplanned data analyses may be required to fulfill regulatory requests. A final analysis for Part A is planned once all participants in Phase 2 complete the study, i.e. Day 91 of follow up. Additional details will be included in the SAP and finalized prior to the database lock for the primary analysis.

## Part B

A single interim analysis is planned after at least 50% of patients enrolled on Part B have completed Day 29 assessments. The interim analysis allows for stopping due to efficacy, to allow for possible accelerated development of ensovibep. A final analysis for Part B will be done once all patients in Phase 3 complete the study, i.e. Day 91 of follow up.

### 4.5 Risks and benefits

**Unmet medical need** - There is an ongoing need for effective antiviral treatment of COVID-19. Vaccines have started to become available, but their ability to prevent transmission or to create long term immunity remains to be determined, their acceptance by the population is currently mixed, their effectiveness against actual and future mutant virus strains is unclear, and – most importantly – their limited availability (in particular, outside the Western World) will result in an ongoing need for therapies for the next 2-3 years or longer. The first monoclonal antibodies targeting SARS-CoV-2 have obtained emergency use authorizations for ambulatory patients with COVID-19 who are at high risk of developing severe COVID-19 and/or hospitalization, but their high cost of production, limited supplies, and the challenges of administration have resulted in very limited use outside clinical trials.

**Potential benefits** - Based on non-clinical studies, ensovibep has the potential to produce antiviral effects which could be beneficial in patients with confirmed SARS-CoV-2 infection as well as prophylactically in subjects at risk of infection. The potential benefits are expected to be related to an early resolution of symptoms and a lower probability of progressing to severe disease requiring hospitalizations or leading to death.

**Potential risks** - Due to its specificity for the virus target and based on non-clinical studies, ensovibep is expected to have an acceptable safety profile. In healthy volunteers, excellent tolerability has been confirmed for 3 mg/kg and 9 mg/kg doses.

However, as ensovibep is a biological agent there is a potential risk of infusion reactions occurring. Consequently, guidance for infusion reaction management is provided in the clinical trial protocol.

There is a potential for patients to develop antidrug antibodies (ADAs), therefore emergence of ADAs will be closely monitored during the study.

The risk to patients in this trial will be minimized by adherence to the eligibility criteria and close clinical monitoring, including by an independent data monitoring committee (IDMC).

**Conclusion** - Taking these potential benefits and risks into consideration, the sponsor is of the opinion that the potential benefits of ensovibep outweigh the potential risks.

Appropriate eligibility criteria and specific dose-limiting toxicity definitions, as well as specific dose modification and stopping rules, are included in this protocol.

The risk to patients in this trial will be minimized by compliance with the eligibility criteria and study procedures, as well as close clinical monitoring. Refer to the IB.

Women of child-bearing potential and sexually active males must be informed that taking the study treatment may involve unknown risks to the fetus if pregnancy were to occur during the study, and agree that in order to participate in the study they must adhere to the contraception requirements outlined in the exclusion criteria.

#### **4.5.1 Blood sample volume**

A volume smaller than a typical blood donation is planned to be collected over a period of 91 days, from each patient as part of the study. Additional samples with a volume smaller than a typical blood donation may be required for safety monitoring.

Timings of blood sample collection are outlined in the assessment schedule ([Table 8-1](#)).

A summary blood log is provided in the laboratory manual. Instructions for sample collection, processing, storage, and shipment information are also available in the Laboratory Manual.

### **5 Study population**

The study will recruit ambulatory symptomatic adult patients diagnosed with COVID-19, with onset of symptoms within 7 days prior to dosing and with a positive rapid antigen test on the day of dosing.

#### **5.1 Inclusion criteria**

Patients eligible for inclusion in this study must meet **all** the following criteria:

1. Men or women  $\geq$  18 years of age on the day of inclusion (no upper limit).
2. Presence of two or more of the following COVID-19 symptoms with an onset within 7 days of dosing: Feeling hot or feverish, cough, sore throat, low energy or tiredness, headache, muscle or body aches, chills or shivering, and shortness of breath.
3. Positive test for SARS-CoV-2 in upper respiratory swab on the day of dosing (rapid antigen test).
4. Understand and agree to comply with the planned study procedures.
5. The patient or legally authorized representative give signed informed consent.

#### **5.2 Exclusion criteria**

Patients meeting **any** of the following criteria are **not** eligible for inclusion in this study.

1. Requiring hospitalization at time of screening, or at time of study drug administration.
2. Oxygen saturation ( $\text{SpO}_2$ )  $\leq$  93% on room air at sea level or ratio of arterial oxygen partial pressure ( $\text{PaO}_2$  in mmHg) to fractional inspired oxygen ( $\text{FiO}_2$ )  $<$  300, respiratory rate  $\geq$  30 per minute, and heart rate  $\geq$  125 per minute.

**In India**, patients with a respiratory rate  $\geq$  24 per minute or with an oxygen saturation  $\leq$  93% on room air ( $\text{SpO}_2$ ) are not eligible.

3. Known allergies to any of the components used in the formulation of the ensovibep or placebo.
4. Suspected or proven serious, active bacterial, fungal, viral, or other infection (besides SARS-CoV-2) that in the opinion of the investigator could constitute a risk when taking intervention.
5. Any serious concomitant systemic disease, condition or disorder that, in the opinion of the investigator, should preclude participation in this study.\*
6. Any co-morbidity requiring surgery within 7 days of dosing, or that is considered life--threatening within 29 days of dosing.
7. Prior or concurrent use of any medication for treatment of COVID-19, including antiviral agents, convalescent serum, or anti-viral antibodies. Purely symptomatic therapies (e.g., over-the-counter [OTC] cough medications, acetaminophen, and nonsteroidal anti-inflammatory drugs [NSAIDs]) are permitted. Prior vaccination for COVID-19 is permitted.
8. Are concurrently enrolled or were enrolled within the last 30 days or within 5 half-lives (whichever is longer) in any other type of medical research judged not to be scientifically or medically compatible with this study.
9. Are pregnant or breast feeding.
10. Women of child-bearing potential, defined as all women physiologically capable of becoming pregnant, unless they are using highly effective methods of contraception at the time of dosing and for 11 weeks after dosing of study drug. Highly effective contraception methods include:
  - a. Total abstinence (when this is in line with the preferred and usual lifestyle of the patient). Periodic abstinence (i.e., calendar, ovulation, symptothermal, and postovulation methods) and withdrawal are not acceptable methods of contraception.
  - b. Female sterilization (have had bilateral surgical oophorectomy [with or without hysterectomy], total hysterectomy, or bilateral tubal ligation at least 6 weeks before taking study treatment). In case of oophorectomy alone, only when the reproductive status of the woman has been confirmed by follow-up hormone level assessment.
  - c. Male sterilization (at least 6 months prior to screening). The vasectomized male partner should be the sole partner for that patient.
  - d. Use of oral, injected, or implanted hormonal methods of contraception or placement of an intrauterine device (IUD) or intrauterine system (IUS) or other forms of hormonal contraception that have comparable efficacy (failure rate < 1%), for example hormone vaginal ring or transdermal hormone contraception.

In case of use of oral contraception, women should have been stable on the same pill for a minimum of 3 months before taking study treatment.

If local regulations deviate from the contraception methods listed above to prevent pregnancy, local regulations apply and will be described in the informed consent form (ICF).

11. For Part A only: Patients in the USA who are at high risk of progression to severe COVID-19 illness or hospitalization\*\* must not be enrolled in Part A of this study as a

placebo-controlled study may not be appropriate in this patient population due to the availability of anti-viral mAbs under EUA in the USA.

\*\* "High risk of progression to severe COVID-19 illness or hospitalization" is defined to match the eligibility criteria for authorized therapy with therapeutic mAbs in the USA, i.e. as meeting at least one of the following criteria: Body mass index (BMI)  $\geq 35$ ; chronic kidney disease; diabetes mellitus; immunosuppressive disease; ongoing immunosuppressive treatment; age  $\geq 65$  years; or age  $\geq 55$  years in a patient with cardiovascular disease, or hypertension, or COPD / other chronic respiratory disease.

\* Co-morbidities defining clinically vulnerable patients (with high risk for progression to serious COVID-19 disease), for example obesity or diabetes, are generally *not* exclusion criteria.

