Key inclusion criteria	
 
1. Men or women <math>\geq 18</math> years of age on the day of inclusion (no upper limit).
 
2. Presence of two or more COVID-19 symptoms and onset within 7 days prior to dosing: Feeling hot or feverish, cough, sore throat, low energy or tiredness, headache, muscle or body aches, chills or shivering, and shortness of breath.
 
3. Positive test for SARS-CoV-2 in upper respiratory swab on the day of dosing (rapid antigen test).
 
4. Understand and agree to comply with the planned study procedures.
 
5. The patient or legally authorized representative give signed informed consent.
 

Key exclusion criteria	
 
1. Requiring hospitalization at time of screening, or at time of study drug administration.
 
2. Oxygen saturation (<math>\text{SpO}_2</math>) <math>\leq 93\%</math> on room air at sea level or ratio of arterial oxygen partial pressure (<math>\text{PaO}_2</math> in mmHg) to fractional inspired oxygen (<math>\text{FiO}_2</math>) <math>< 300</math>, respiratory rate <math>\geq 30</math> per minute, and heart rate <math>\geq 125</math> per minute.
 
 
In India, patients with a respiratory rate <math>\geq 24</math> per minute or with an oxygen saturation <math>\leq 93\%</math> on room air (<math>\text{SpO}_2</math>) are not eligible.
 
 
3. Known allergies to any of the components used in the formulation of the ensovibep or placebo.
 
4. Suspected or proven serious, active bacterial, fungal, viral, or other infection (besides SARS-CoV-2) that in the opinion of the investigator could constitute a risk when taking intervention.
 
5. Any serious concomitant systemic disease, condition, or disorder that, in the opinion of the investigator, should preclude participation in this study.
 
6. Any co-morbidity requiring surgery within 7 days of dosing, or that is considered life-threatening within 29 days of dosing.
 
7. Prior or concurrent use of any medication for treatment of COVID-19, including antiviral agents, convalescent serum, or anti-viral antibodies. Purely symptomatic therapies (e.g., over-the-counter [OTC] cough medications, acetaminophen, and nonsteroidal anti-inflammatories [NSAIDs]) are permitted. Prior vaccination for COVID-19 is permitted.
 

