**Table 8-1 Part A: Assessment schedule**

Visit Name	S1 [6]	V1		V2	V3	V4	V5	V6	V7	V8	V9
Study Day	-3 to -1	1		3	5	8 ± 2	15 ± 3	22 ± 4	29 ± 5 (EOS) [7]	61 ± 5	EOS[8] / 91 ±7
		pre-dose	post-dose								
STUDY ENTRY AND GENERAL ASSESSMENTS											
Informed consent	(X)	X									
Inclusion/Exclusion criteria	(X)	X									
Demographics	(X)	X									
Complete medical history	(X)	X									
INVESTIGATIONAL PRODUCT											
Ensovibep (MP0420)/Placebo			X								
SAFETY ASSESSMENTS											
Prior/concomitant medication evaluation	Continuous starting after ICF signature, until 3 months after study medication										
Prior/concomitant hospitalization and procedures	Continuous starting after ICF signature, until 3 months after study medication										
AE evaluation	Continuous starting after ICF signature, until 3 months after study medication										
Local tolerability			X								
Physical examination and vital signs [1]	(X)	X									
General physical appearance and vital signs [1]				X	X	X	X		X		X
Body temperature, respiratory rate, oximetry	(X)	X		X	X	X	X		X		X

Visit Name	S1 [6]	V1		V2	V3	V4	V5	V6	V7	V8	V9
Study Day	-3 to -1	1		3	5	8 ± 2	15 ± 3	22 ± 4	29 ± 5 (EOS) [7]	61 ± 5	EOS[8] / 91 ±7
		pre-dose	post-dose								
Weight	(X)	X									X
Height	(X)	X									
Hematology, chemistry and coagulation safety tests		X		X			X		X	X	X
Pregnancy test in WOCBP [2]	(X)	X									X
Birth Control	Continuous until EOS [3]										
	VIROLOGY & SEROLOGY ASSESSMENTS										
Rapid SARS-CoV-2 antigen test	(X)	X									
SARS-CoV-2 sample (quantitative RT-PCR, mutation analysis)		X		X	X	X	X		X		X
PK blood sample		X	XX [4]	X		X	X		X	X	X
Blood sample for serum biomarkers		X		X		X	X		X		X
	CLINICAL ASSESSMENTS										
Symptom score [5]		X		Daily assessment				X	X		

Visit Name	S1 [6]	V1		V2	V3	V4	V5	V6	V7	V8	V9
Study Day	-3 to -1	1		3	5	8 ± 2	15 ± 3	22 ± 4	29 ± 5 (EOS) [7]	61 ± 5	EOS[8] / 91 ±7
		pre-dose	post-dose								

[REDACTED]; AE=adverse event; EOS=end-of-study; FDA=Food and Drug Administration; ICF=informed consent form; PCR=polymerase chain reaction; PK=pharmacokinetics; PRO=patient-reported outcome; RT=reverse transcriptase; S=screening; [REDACTED]; V=visit; WOCBP=women of child-bearing potential.

1. Vital signs consist of systolic and diastolic blood pressure and heart rate.

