## 8.4 Safety

Safety assessments are specified below with the assessment schedule detailing when each assessment is to be performed.

For details on AE collection and reporting, refer to AE section.

Assessment	Specification
Physical examination	
A complete physical examination (Day 1) will include the examination of general appearance, skin, neck (including thyroid), eyes, ears, nose, throat, lungs, heart, abdomen, back, lymph nodes, extremities, vascular, and neurological. If indicated based on medical history and/or symptoms, rectal, external genitalia, breast, and pelvic exams will be performed.
 
An assessment of general physical appearance will include the examination of general appearance and vital signs (systolic and diastolic blood pressure [BP], heart rate [HR], temperature and pulse oximetry). An assessment of general physical appearance will be performed at all visits starting from Day 3.
 
Information for all physical examinations must be included in the source documentation at the study site. Clinically relevant findings that are present prior to signing informed consent must be recorded on the appropriate CRF that captures medical history. Significant findings made after signing informed consent which meet the definition of an Adverse Event must be recorded as an adverse event.

Vital signs	
Vital signs will include the collection of BP and HR. After the patient has been sitting for 3 minutes, with back supported and both feet placed on the floor, systolic and diastolic BP will be measured using an automated validated device, e.g., OMRON with an appropriately sized cuff. In case the cuff sizes available are not large enough for the patient's arm circumference, a sphygmomanometer with an appropriately sized cuff may be used.
 
If vital signs are out-of-range at screening and/or baseline (see Section 5.2 of the protocol for details), two additional readings can be obtained, so that a total of three consecutive assessments are made, with the patient seated quietly for approximately five minutes preceding each repeat assessment. The last reading must be within the ranges provided in the eligibility criteria in order for the patient to qualify.
 
In case of repeated vital assessments, the eCRF should contain all repeat measurements.

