Temperature, respiratory rate and oximetry	Body temperature (in °C), respiratory rate and oxygen saturation (pulse oximeter) will be assessed simultaneous to vital signs.
Height and weight	
Height in centimeters (cm) and body weight (to the nearest 0.1 kilogram [kg] in indoor clothing, but without shoes) will be measured as specified in Table 8-1 and Table 8-2.
 
Body mass index (BMI) will be calculated using the following formula:
 $\text{BMI} = \text{Body weight (kg)} / (\text{Height [m]})^2$

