5.3 Derivation of baseline COVID-19 severity

Baseline COVID-19 severity will be calculated based on the FDA guidance ([CDER 2020b](#)). Derivation for severe or critical COVID-19 are not included as these patients will not be enrolled in the trial.

Mild COVID-19:

- No presence of dyspnea (as found in the eCRF); AND,
- Respiratory rate < 20 breaths/minute; AND,
- Heart rate < 90 beats/minute.
- AND no criterion for moderate or severe COVID-19

Moderate COVID-19:

- Presence of dyspnea with exertion (as found in the eCRF); OR,
- Respiratory rate 20 - < 30 breaths/minutes; OR,
- Heart rate 90 - < 125 beats/minute
- AND no criterion for severe COVID-19.

Severe COVID-19:

- Presence of dyspnea at rest (as found in the eCRF); OR,
- Respiratory rate \geq 30 breaths/minutes; OR,
- Heart rate \geq 125 beats/minute; OR
- Oxygen saturation SpO₂ \leq 93%

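### Exclusion criterion 2 mixes *or* and *and*, so read literally outside India it does not by itself exclude a respiratory rate ≥30 alone, which the SAP classes as severe

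*Protocol*

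**What the plan says.** Protocol 5.2 excludes a patient who meets any numbered criterion. Inside criterion 2 the limits are SpO2 ≤93% on room air at sea level *or* PaO2/FiO2 <300, then respiratory rate ≥30, with the last two joined as "30 per minute, and heart rate" ≥125. The Protocol summary has the same connector: "per minute, and heart rate". A separate sentence for India excludes a respiratory rate ≥24 *or* SpO2 ≤93%. The India amendment rationale limits that change to India.

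SAP 5.3 classes a patient as severe on any one of four findings: dyspnea at rest, respiratory rate ≥30, heart rate ≥125 or SpO2 ≤93%. The same section says "Derivation for severe or critical COVID-19 are not included as these patients will not be enrolled in the trial". SAP 2.3.2 nevertheless keeps a severe category in the baseline table in case one appears.

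The vital signs row of Protocol 8.4 refers out-of-range readings to Section 5.2, allows repeats, and states: "The last reading must be within the ranges provided in the eligibility criteria in order for the patient to qualify".

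**The concern.** The *any* in the lead-in to Protocol 5.2 chooses among numbered criteria. It does not say how the limits inside criterion 2 combine, and the sentence that should say so uses both connectors. Two literal readings are possible: (a) every limb is required, or (b) SpO2 ≤93% excludes alone and the other three are required together. Under neither does criterion 2, taken by itself, exclude a patient whose only breach is a respiratory rate ≥30.

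This is an operative safety rule in a placebo-controlled outpatient trial. Protocol 11.3 requires full verification of adherence to the eligibility criteria, but that check is made against this same sentence, so monitoring would not expose the ambiguity.

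**Working it through.** There is no planned figure to reproduce. The check is a count of logical patterns.

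**Inputs.** S = SpO2 ≤93%, P = PaO2/FiO2 <300, R = respiratory rate ≥30, H = heart rate ≥125 (Protocol 5.2). Severe means S or R or H (SAP 5.3, setting dyspnea at rest aside because criterion 2 has no such limit). Severe patterns in S, R and H: 2³ − 1 = 7.

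**Readings of criterion 2.**
- (a) (S or P) and R and H.
- (b) S or (P and R and H).
- (c) S or P or R or H, the evident intent.

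**What Protocol 8.4 adds.** Its within-range rule applies to vital signs, and the documents define these in three ways:
- Narrow list. The vital signs row says "Vital signs will include the collection of BP and HR", and Table 8-1 footnote 1 says "Vital signs consist of systolic and diastolic blood pressure and heart rate". Section 5.2 has no blood pressure limit, so the rule bites on heart rate: H disqualifies alone. Respiratory rate and oximetry have their own row, where "respiratory rate and oxygen saturation (pulse oximeter) will be assessed simultaneous to vital signs".
- Wider Protocol list. The physical examination row of 8.4 gives blood pressure, then "heart rate [HR], temperature and pulse oximetry". This adds SpO2 but not respiratory rate.
- SAP list. SAP 2.8.4.1 and the notable-value table in SAP 5.6 count both respiratory rate and oxygen saturation as vital signs.

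**Count outside India, no blood gas (P = 0).** On every list H excludes alone, which removes 4 of the 7 patterns (H, S+H, R+H, S+R+H) and leaves S, R and S+R. The patterns still eligible are:

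| Vital-sign list applied to 8.4 | Reading (a) | Reading (b) |
|---|---|---|
| Narrow (heart rate) | 3 of 7: S; R; S+R | 1 of 7: R |
| Wider Protocol (plus SpO2) | 1 of 7: R | 1 of 7: R |
| SAP (plus SpO2 and respiratory rate) | 0 of 7 | 0 of 7 |

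Under reading (c) the count is 0 of 7. In India it is also 0 of 7, because the local sentence excludes S and R alone and 8.4 excludes H.

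**If a blood gas is available.** P can be 0 or 1, so there are 7 × 2 = 14 patterns. On the narrow list (a) leaves 3 × 2 = 6 of 14 and (b) leaves 1 × 2 = 2 of 14. Reading (c) leaves 0 of 14.

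**Criterion 2 with 8.4 ignored.** Reading (a) excludes only patterns with R and H and at least one of S and P, which is 3, leaving 14 − 3 = 11 of 14. Reading (b) excludes the 8 patterns with S plus the one with P, R and H and no S, leaving 14 − 9 = 5 of 14.

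**The case against.** The strongest reply is that 8.4 already closes the gap. It speaks of ranges in the plural, although on the narrow list Section 5.2 supplies only one. Respiratory rate is measured together with the vital signs, and the SAP counts it as one. On that view nothing is open. This stands as an arguable reading, and it is why the range starts at 0. It does not settle the matter: Table 8-1 footnote 1 confines vital signs to blood pressure and heart rate, and the SAP lists serve analysis and reporting rather than site screening.

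A second reply is that the literal readings are strained. Reading (a) would keep a patient with low SpO2 eligible unless both other rates were also breached. Reading (b) would make the respiratory rate limit depend on a blood gas that Table 8-1 does not schedule. Sites may well have taken the sentence as a list of separate limits. That is fair, and it supports rewriting the sentence to say so.

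Criterion 1 (needing hospitalization) and criterion 5 (investigator judgement on serious concomitant conditions) are further backstops, but neither sets a vital-sign threshold.

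A reader might go further and infer that severe patients were enrolled, that a respiratory rate ≥30 is certainly admitted, or that 11 of 14 severe patterns are open. The documents support none of these. They give no count of such patients, the vital-sign lists conflict, and the 11 of 14 ignores the 8.4 rule that makes heart rate disqualify alone.

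**Conclusion.** The wording is defective and worth correcting before Part B. The India text, the within-range rule in 8.4 and SAP 5.3 all point to *any one limit excludes*, and criterion 2 does not say that. Outside India, 0 to 3 of the 7 patterns stay open, depending on the reading of criterion 2 and on which vital-sign list governs 8.4.

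The counts assume no blood gas. Table 8-1 supports this for Part A. It is an assumption for Part B, because the content of Table 8-2 is not in the available text. The counts are patterns, and the number of patients affected cannot be derived. No power, alpha or primary-model result changes. The global amendment records 381 patients treated by 19-Oct-2021 against a Part A target of at least 400, so the benefit falls mainly on the 1717 patients planned for Part B.

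It would also be too strong to say that repairing criterion 2 makes the SAP 5.3 statement about enrolment true. SAP 5.3 counts dyspnea at rest as severe and criterion 2 has no such limit, so a patient severe by the SAP could still enter.

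**What to change.** Before Part B, restate criterion 2 in Protocol 5.2 and in the Protocol summary so that any one of these excludes:
- SpO2 ≤93% on room air at sea level (in India, on room air); or
- PaO2/FiO2 <300; or
- respiratory rate ≥30 per minute (in India, ≥24); or
- heart rate ≥125 per minute.

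In SAP 5.3, delete the sentence saying that severe derivations are left out because such patients will not enter. The section goes on to define severe, including dyspnea at rest, and SAP 2.3.2 already provides for the category.

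The cost is one sentence in two places in the next protocol amendment, a note to sites, and one line in the SAP amendment already planned before the first Part B patient. No procedure is added.
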